1.2.4. Revision History for SAP Amendments

NA

2. INVESTIGATION PLAN

2.1. Study Design and Randomization

This is a Phase 2, multicenter, randomized, double-blind, parallel-group, 2-arm study in subjects aged 6 to 17 years inclusive who are allergic to peanut. The study consists of a screening period of up to 16 weeks, a 28 to 40-week double-blind treatment period, a 24-week maintenance phase, and a 12-week post-treatment follow-up period. In protocol amendment 3 to accommodate COVID-19 restrictions, double-blind treatment period was extended from 28 weeks to up to 40 weeks. Subjects who attend optional visits between week 28 and week 40 will have increased duration of exposure to AR101 and dupilumab.

Approximately 156 subjects will be randomized at baseline in a 2:1 ratio into one of 2 treatment arms (n=104 to dupilumab and 52 to placebo, in combination with up-dosing of AR101) according to a central randomization scheme provided by an IWRS. Randomization will be stratified by screening peanut-specific IgE level ($\leq 100 \text{ kUA/L}$ or $\geq 100 \text{ kUA/L}$) and body weight ($\leq 30 \text{ kg}, \geq 30 \text{ kg}$ and $\leq 60 \text{ kg}$, or $\geq 60 \text{ kg}$) at randomization. A minimum of 15 subjects for each weight group will be enrolled.

At visit 16 (or at the early termination visit for those who discontinue from study prior to visit 16), subjects previously in the dupilumab plus AR101 arm will be re-randomized in a 1:1 ratio into one of 2 treatment arms (dupilumab versus placebo, in combination with AR101), according to a central randomization scheme provided by IWRS. Randomization will be stratified by whether subjects achieve 300 mg/day AR101 for at least 2 weeks by visit 16 (Yes or No).

Subjects previously in the placebo plus AR101 arm will continue their treatment of placebo plus AR101 in the maintenance phase if they achieve 300 mg/day AR101 for at least 2 weeks at visit 16.

2.2. Statistical Hypothesis

The primary efficacy endpoint is the proportion of subjects who achieve a cumulative dose of 2044 mg peanut protein during a post up-dosing DBPCFC at visit 16. The comparison between the dupilumab + AR101 arm and the placebo + AR101 arm will be made.

Let p_D and p_P be the true proportions of subjects who achieve a cumulative dose of 2044 mg of peanut protein during a post up-dosing DBPCFC at visit 16 in the treatment arms of dupilumab + AR101 and placebo + AR101, respectively. The following hypothesis for the superiority testing will be tested at the 5% 2-sided significance level for the up-dosing phase:

H0: $p_D = p_P$, i.e., the proportion of subjects who achieve a cumulative dose of 2044 mg peanut

protein during a DBPCFC at visit 16 is the same between dupilumab + AR101 arm and the placebo + AR101 arm

against the alternative

Ha: $p_D \neq p_P$, i.e., the proportion of subjects who achieve a cumulative dose of 2044 mg peanut protein during a DBPCFC at visit 16 are different between the dupilumab + AR101 arm and the placebo + AR101 arm

CONFIDENTIAL

Page 13 of 86

2.3. Sample Size and Power Considerations

It is assumed that the proportion of subjects who achieve a cumulative dose of 2044 mg of peanut protein during a post up-dosing DBPCFC at visit 16 in placebo plus AR101 arm will be 40%, based on an Aimmune presentation at the 2018 American Academy of Allergy, Asthma & Immunology–World Allergy Organization Joint Congress; with the proportion of subjects in dupilumab plus AR101 arm assumed to be 65%, which is considered to be clinical meaningful benefit by adding on dupilumab treatment. A sample size of approximately 156 subjects (104 in dupilumab plus AR101 and 52 in placebo plus AR101) will have 80% power to detect the treatment difference of 25% between placebo plus AR101 and dupilumab plus AR101 at the 2-sided 5% significance level (the minimum significant difference is approximately 17.8%). The sample size calculations were done by Fisher exact test using nQuery (7.0).

[figure not shown]
Approximately 122 subjects who undergo the post up-dosing DBPCFC at Week 28 (visit 16 with a window of -7/+30 days) as per protocol or discontinue from study prior to Week 28 (visit 16 with a window of -7/+30 days) will be included in the primary efficacy analysis. These subjects receive AR101 dose escalation per the original protocol's 24-week up-dosing schedule. The minimum significant difference with approximately 122 subjects is approximately 20.7% between placebo plus AR101 and dupilumab plus AR101 assuming placebo plus AR101 treatment effect is 40% at the 2-sided Fisher exact test with 5% significance level.

2.4. Study Plan

The study consists of a screening period of up to 16 weeks, a 28 to 40-week double-blind treatment period, which includes 4 weeks of pretreatment with dupilumab or placebo followed by 24 to 36 weeks of treatment with dupilumab or placebo in combination with a gradual up-dosing of AR101, a 24-week maintenance phase with 300 mg/day AR101 with concomitant dupilumab or matching placebo (for subjects who achieve 300 mg/day AR101 for at least 2 weeks in the up-dosing period), and a 12-week post-treatment follow-up period (Figure 1). Subjects who do not achieve 300 mg/day will still enter the 12-week follow-up. Excluding the screening period, the duration of the study is approximately 64 to 76 weeks for subjects who enter the maintenance period, and 40 to 52 weeks for subjects who do not achieve 300 mg/day AR101 for at least 2 weeks at visit 16 and do not enter the maintenance period.

Figure 1. Schematic of Study Design

Enroll 2-arms (2:1), up-dose AR101 from week 4 to week 28 to 40. Subjects in DUP (dupilumab) +AR101 group will be rerandomized to DUP+AR101 and PBO (placebo) + AR101, but only those subjects who achieve 300 mg/day AR101 for at least 2 weeks will be eligible to enter the 24-week maintenance treatment. Subjects who do not achieve 300 mg/day AR101-CODIT will enter a 12-week follow-up.

During screening visit 1 (Day -113 to day -17), subjects will undergo a medical history, physical examination, spirometry, a standard peanut skin prick test (SPT), and laboratory testing (including peanut sIgE), and will be evaluated for the study eligibility criteria. Subjects must meet all eligibility for Screening Visit 1 before proceeding with the DBPCFC in Visit 1a, which will consist of 5 doses of peanut or placebo oat protein given every 15 to 30 minutes in increasing amounts up to a cumulative total of 144 mg of peanut protein. The doses will be 1, 3, 10, 30 and 100 mg. If the study team suspects a reaction may be developing, they may exercise their clinical judgment to separate doses by up to an additional 30 minutes (1-hour maximum between doses). The food challenges will be performed on different days (1-day placebo [oat] protein, 1-day peanut protein, with order determined at random) at least 24 hours apart. Both food challenge days (placebo and peanut) must be done. Subjects will be considered to have tolerated the DBPCFC if they do not experience any objective Grade 1 (mild) reaction by the Consortium of Food Allergy Research (CoFAR) grading system to the peanut protein ingestion \leq 144 mg (cumulative) or experience any symptoms at any dose of placebo and will be excluded from the study.

Subjects with a history of confirmed peanut allergy who continue to meet eligibility criteria at baseline will undergo Day 1/baseline assessments and will be randomized in a 2:1 ratio stratified by screening peanut-specific IgE level ($\leq 100 \text{ kUA/L}$ or >100 kUA/L) and body weight (< 30 kg, $\geq 30 \text{ kg}$ and < 60 kg, or $\geq 60 \text{ kg}$) at randomization into one of 2 Treatment Arms (104 for dupilumab and 52 for placebo). A minimum of 15 subjects for each weight group will be enrolled.

Dupilumab and placebo will be dosed subcutaneously (SC) as follows based on weight at randomization and dose will not be changed regardless of weight gain or loss:

• subjects weighing <30 kg will receive dupilumab 100 mg every 2 weeks (Q2W) following a loading dose of 200 mg or matching placebo Q2W

CONFIDENTIAL

Page 15 of 86

Regeneron Pharmaceuticals, Inc. Statistical Analysis Plan

- subjects weighing ≥30 kg and <60 kg will receive dupilumab 200 mg Q2W following a loading dose of 400 mg or matching placebo Q2W
- subjects weighing ≥60 kg will receive dupilumab 300 mg Q2W following a loading dose of 600 mg or matching placebo Q2W

After the first 4 weeks, subjects will begin AR101 with an up-dosing regimen to a maximum of 300 mg/day over the next 24 to 36 weeks of the study, for a total of 28 to 40 weeks (including pretreatment) with 28 weeks being ideal and 40 weeks being the maximum. (The flexible up-dosing period is to accommodate COVID-19 restrictions of in-clinic visits, as well as dose reductions and re-escalation, if necessary). Thus, the up-dosing period will consist of 4 weeks pretreatment, 22 to 34 weeks of flexible up-dosing, and at least 2 weeks at the maximum dose of 300 mg/day. During concomitant AR101, study drug will be administered SC at home (at least 24 hours after in-clinic AR101 dose escalation and at least 8 hours apart from the at-home daily AR101 dose). All subjects will go up to visit 15 (Week 26). Visits 15a-f (Week 28 to 38) will be optional in order to reach 300mg/day AR101 for a minimum of 2 weeks. Subjects will undergo a post up-dosing DBPCFC at visit 16 if they have reached 300 mg/day for at least 2 weeks (on a day after the last dose of AR101). Dosing with AR101 should continue on the days between the two parts of the DBPCFC.

Starting on Day 1, subjects will have weight-based dose of placebo or dupilumab Q2W SC for 28 to 40 weeks. At Week 4, all subjects will be administrated AR101 using a standardized regimen of single initial dose escalation day (IDED) from 0.5 mg to a maximum of 6 mg peanut protein (12 mg cumulative) over 5 hours in-clinic (home dosing will be 3 mg peanut protein every evening for the next 2 weeks until up-dosing) (Table 1) followed by bi-weekly in-clinic up-dosing from the highest tolerated initial day dose to a maximum of 300 mg/day at home for 22 to 34 additional weeks. If the scheduled bi-weekly up-dosing is not possible, the up-dosing period may be extended by up to 12 weeks to accommodate COVID-19 restrictions of in-clinic visits, as well as dose reductions and re-escalation, if necessary. Thus, the up-dosing period will end at Week 28 to 40 (including 4 weeks pretreatment, 22 to 34 weeks of flexible up-dosing, and at least 2 weeks at the maximum dose).

| | Dupilumab/Placebo + AR101 |
|------------------------|---------------------------|
| Week 4 (1 to 5 h) IDED | Dose of Protein (mg) |
| Q30 min | 0.5 |
| | 1 |
| | 1.5 |
| | 3 |
| | 6 |
| Cumulative | 12 |

Table 1:AR101 Initial Dose Escalation Day at Week 4

Abbreviations: IDED, initial dose escalation day; Q30, every 30 min

At visit 16, subjects who achieve 300 mg/day of AR101 for at least 2 weeks will undergo a post up-dosing DBPCFC to assess the level of peanut sensitivity. And all dupilumab group subjects will be re-randomized 1:1 to placebo or dupilumab. Only subjects from either treatment group who achieve 300 mg/day AR101 at visit 16 will be eligible to enter the maintenance phase, in which subjects will continue to receive AR101 300 mg/day for 24 weeks. Subjects who do not achieve 300 mg/day AR101 for at least 2 weeks will enter a 12-week follow-up period. In the analysis, subjects not achieving 300mg for a least 2 weeks are considered as the non-responders in DBPCFC. Placebo group subjects will continue to receive placebo in the maintenance phase. At visit 22, subjects will undergo a DBPCFC to access the level of peanut sensitivity at the end of maintenance period.

The post up-dosing and post maintenance DBPCFCs will consist of 8 doses (peanut or placebo) given every 15 to 30 minutes: 1, 3, 10, 100, 300, 600, 1000 mg resulting in a total challenge of up to 2044 mg.

All subjects will have a 12-week follow-up period after the end of treatment and will undergo safety, laboratory, and clinical assessments. At the end of the 12-week follow-up period, subjects who passed a 444 mg (cumulative) peanut protein DBPCFC at visit 22 (end of maintenance period, Week 52 to 64) will be eligible to undergo a final DBPCFC (up to 2044 mg cumulative) under intensive monitoring, at visit 25 (end of study, Week 64 to 76) to assess the level of peanut sensitivity after 12 weeks off peanut and dupilumab to determine whether there is evidence of persistent effects and sustained unresponsiveness.

3. ANALYSIS POPULATIONS

In accordance with guidance from the International Conference of Harmonization of Technical Requirements for Registration of Pharmaceuticals for Human Use (ICH) guideline ICH E9 Statistical Principles for Clinical Trials (ICH, 1998), the following population of analysis will be used for all statistical analysis:

3.1. The Full Analysis Set (FAS)

FAS includes all randomized subjects. Efficacy analyses will be based on the treatment allocated by the IWRS at randomization (as randomized).

The modified full analysis set (mFAS) includes all FAS subjects who undergo bi-weekly in-clinic up-dosing as described/specified in the protocol and undergo the post up-dosing DBPCFC at Visit 16/Week 28 (a window of -7/+30 days).

The mFAS will be considered as primary analysis set for all efficacy endpoints. The FAS will also be done for all efficacy endpoints as supportive analyses.

FAS-maintenance is a subset of FAS and includes subjects in the FAS who achieve 300 mg/day AR101 for at least 2 weeks in the up-dosing phase and re-randomized based on the treatment allocated by the IWRS at visit 16. The FAS-maintenance is the primary analysis set for efficacy analyses at visit 22.

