Updated sample size for the primary analysis such that approximately 122 subjects who undergo the post up-dosing double-blind placebo-controlled food challenge (DBPCFC) at week 28 (visit 16) or discontinue from study prior to week 28 (visit 16) will be included in the primary efficacy analysis. Added a new analysis set to the statistical plan to clarify that these subjects who up-dosed AR101 per the original protocol plan will be analyzed in a modified full analysis set (mFAS), separate from the full analysis set (FAS), which includes all randomized subjects.	To differentiate the analysis of subjects who up-dosed AR101 per the original protocol plan from those subjects who attended optional visits 15a-f (added in amendment 3 to accommodate COVID-19 restrictions), which extended up-dosing by up to 12 weeks. Subjects who attend optional visits will have increased duration of exposure to AR101 and dupilumab.	Clinical Study Protocol Synopsis: Statistical Plan Section 11.2 Justification of Sample Size Section 11.3.1 Efficacy Analysis Sets Section 11.4.1 Subject Disposition Section 11.4.3 Efficacy Analyses Section 11.4.3.1 Primary Efficacy Analysis
Clarified that several treatments listed in prohibited medications are also considered rescue treatments and should result in study discontinuation, whereas acute treatment with epinephrine and certain other medications is permitted for the treatment of allergic reactions.	For clarification that certain rescue medications will lead to study drug discontinuation as they may affect study outcome.	Section 8.2 Rescue Treatment Section 8.3.2.1 Reasons for Permanent Discontinuation of Study Drug Section 8.7 Concomitant Medications Section 8.7.1 Prohibited Medications and Procedures

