6.1.1. Description of AR101 Dose Escalation, and Study Stopping Rules

6.1.1.1. AR101 Initial Dose Escalation Day at Week 4

The IDED will be done in-clinic at week 4 and consist of AR101 dosing, beginning at 0.5 mg of AR101 with graduated doses every 30 minutes up to 6 mg (cumulative 12 mg) over 5 hours (see Table 1 and Appendix 4). Subjects must be stable, with stable lung function, FEV1 >80% predicted, without evidence of wheezing on exam, or active allergic symptoms such as AD or symptoms of allergic rhinitis or any other symptoms that in the clinical judgement of the study physician contradicts initial dosing.

Trained clinical staff will be present at all times during all of the in-clinic AR101 dosing visits and will be available to respond within minutes to any allergic reaction. Allergic events (Appendix 2) will be monitored for at least 2 hours after the last dose or for at least 2 hours after resolution of symptoms prior to discharge from the clinic. Subjects tolerating the escalation dose will continue to administer a 3 mg/day dose at home for the next 14 days. Subjects who do not tolerate the 6 mg single dose (12 mg cumulative) during IDED, due to moderate or severe allergic reactions

(Appendix 4), will be considered treatment failures and will not initiate home AR101 dosing and should be early terminated from the study.

6.1.1.2. AR101 Up-Dosing Regimen Starting at Week 6

Subjects in the placebo and dupilumab treatment groups will have bi-weekly in-clinic visits with bi-weekly dose increases of the daily oral home AR101 dose from 3 mg/day up to a maximum of 300 mg/day by week 24 to 36 (see Table 2) depending on safety (see Appendix 5). Subjects who exhibit moderate symptoms (Appendix 2) may have the dose reduced by 1 dose level per visit (ie, go back to the previous dose prior to new up-dose) until dose tolerated with no or mild symptoms (see Appendix 5). A dose reduction, at the investigator's discretion, may also be implemented for an intercurrent adverse event. Subjects who exhibit severe allergic symptoms (Appendix 2) must be discontinued from study drug (see Appendix 5).

Note: As of Amendment 3, the up-dosing period has been extended to accommodate dose reductions and re-escalation as well as COVID-19 restrictions of in-clinic visits. This extension permits a maximum up-dosing period of 40 weeks, while 28 weeks is ideal (consisting of 4 weeks pretreatment, 22 to 34 weeks of up-dosing, and at least 2 weeks at the maximum dose.)

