11.2. Justification of Sample Size

It is assumed that the proportion of subjects who achieve a cumulative dose of 2044 mg of peanut protein during a post up-dosing DBPCFC at visit 16 in the placebo plus AR101 arm will be 40%, based on an Aimmune presentation at the 2018 American Academy of Allergy, Asthma & Immunology–World Allergy Organization Joint Congress; with the proportion of subjects in the dupilumab plus AR101 arm assumed to be 65%, which is considered to be clinical meaningful benefit by adding on dupilumab treatment. A sample size of approximately 156 subjects (104 in dupilumab plus AR101 and 52 in placebo plus AR101) will have 80% power to detect the treatment difference of 25% between placebo plus AR101 and dupilumab plus AR101 at the 2-sided 5% significance level (the minimum significant difference is approximately 17.8%). The sample size calculations were done by Fisher exact test using nQuery (7.0).

Approximately 122 subjects who undergo the post up-dosing DBPCFC at week 28 (visit 16 with a window of -7/+30 days) or discontinue from study prior to week 28 (visit 16 with a window of -7/+30 days) will be included in the primary efficacy analysis. These subjects receive AR101 dose escalation per the original protocol's 24-week up-dosing schedule. The minimum significant

difference with approximately 122 subjects is approximately 20.7% between placebo plus AR101 and dupilumab plus AR101 assuming the placebo plus AR101 treatment effect is 40% at the 2-sided Fisher exact test with 5% significance level.

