11.3. Analysis Sets

11.3.1. Efficacy Analysis Sets

The full analysis set (FAS) includes all randomized subjects. Efficacy analyses will be based on the treatment allocated at randomization (as randomized).

The modified full analysis set (mFAS) includes all FAS subjects who undergo the post up-dosing DBPCFC at week 28 (visit 16 with a window of -7/+30 days) or discontinue from study prior to week 28 (visit 16 with a window of -7/+30 days).

The mFAS will be used for primary analysis for all efficacy endpoints. Analysis of the FAS will also be done for supportive analyses.

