Peanut allergy is an immunoglobulin E (IgE)- mediated hypersensitivity reaction following the ingestion of normally innocuous peanut protein. Cross-linking of peanut-specific IgE (sIgE) bound to high affinity IgE receptors on mast cells and basophils triggers immediate degranulation. Subsequent release of a diverse array of inflammatory mediators results in severe allergic symptoms such as hives, wheezing, vomiting and, in severe cases, anaphylactic shock. Release of these mediators also initiates Type 2 T-helper cell (Th2) cytokine release, which results in eosinophil infiltration and creates a vicious cycle of chronic allergic inflammation. Like other forms of allergy immunotherapy, OIT to peanut involves a slow up-dosing of exposure to allergen, in this case peanut, over time to desensitize or increase the threshold of reactivity to peanut. Once reaching a target level of peanut protein, subjects are continued on a maintenance dose of peanut protein to maintain desensitization. Although many subjects on a maintenance dose of peanut

CONFIDENTIAL

Page 8 of 86

protein have demonstrated desensitization to peanut (i.e., the ability to tolerate a level of exposure to peanut without an allergic reaction), up to 80% of subjects exhibit related adverse events (AEs) during OIT, with 42% experiencing systemic reactions and 49% experiencing gastrointestinal (GI) symptoms; the majority of these are mild and decline with prolonged treatment (Virkud, 2016). Up to 20% of subjects, however, are unable to complete the up-dosing regimen due to side effects, which are primarily GI related. An additional issue with current OIT is its limited ability to induce clinical tolerance when subjects are taken off daily peanut intake (Vickery, 2014). In many of the studies with peanut OIT, despite years of immunotherapy, subjects never achieve tolerance and are re-sensitized within weeks of halting daily peanut intake, with a small percentage (~10%) maintaining a sustained unresponsiveness even after 3 months off OIT.

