4.5. Efficacy Variable

4.5.1. **Primary Efficacy Variable (s)**

The primary endpoint in this study is:

• Proportion of subjects treated with dupilumab plus AR101 vs placebo plus AR101 who "pass" a post up-dosing DBPCFC with 2044 mg (cumulative) peanut protein at visit 16

Double-blind placebo-controlled food challenge (DBPCFC)

At visit 16, under intensive monitoring, all subjects who achieve 300 mg/day AR101 during the up-dosing phase for at least 2 weeks will undergo a post up-dosing DBPCFC up to 2044 mg (cumulative) peanut protein or placebo to assess desensitization. At visit 22, all subjects who maintain 300 mg/day AR101 will undergo a post maintenance DBPCFC up to 2044 (cumulative) peanut protein or placebo to assess desensitization. The subject's sensitivity to peanut allergen is defined as the dose at which the subject experiences allergic reactions. All symptoms and signs will be evaluated and rated based on a standardized oral food challenge scoring system (CoFAR). Up-dosing during the DBPCFC will be stopped when the principal investigator (or designee) finds symptoms and/or signs that indicate a definite objective (Grade 1 [mild]) allergic reaction (CoFAR grading system) has occurred based on clinically significant changes in reported symptoms, physical findings, or vital signs that the subject is experiencing to the challenge material. Vital signs will be assessed every 15 to 30 minutes. In addition, subjects will be considered to have dose-limiting reactions if they experience any mild subjective reactions requiring pharmacologic intervention and/or any moderate/severe reaction.

The DBPCFC will consist of 8 doses (peanut protein or placebo), given every 15 to 30 minutes: 1, 3, 10, 30, 100, 300, 600, 1000 mg, up to 2044 mg peanut protein (cumulative). Both peanut and oat protein will be concealed in a food that masks the taste. The food challenge will be performed on different days (1-day placebo [oat] protein, 1-day peanut protein, with order determined at random) at least 24 hours, but not more than 7 days apart, and not within 24 hours of a dose of study drug. Subjects will be considered to have passed the DBPCFC if they do not experience any objective Grade 1 (mild) reaction by CoFAR grading system. If the subject experiences reactions,

Regeneron Pharmaceuticals, Inc. Statistical Analysis Plan

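### SAP 3.1 leaves subjects who quit the study before week 28 out of the primary analysis set, contrary to protocol 11.2, protocol 11.3.1 and SAP 2.3

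*SAP*

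**What the plan says.** **SAP 3.1** states that the mFAS "includes all FAS subjects who undergo bi-weekly in-clinic up-dosing as described/specified in the protocol and undergo the post up-dosing DBPCFC" at visit 16/week 28 (-7/+30 days). It makes the mFAS the primary set for every efficacy endpoint and the FAS (all randomised) supportive. A subject must meet both conditions, and there is no branch for someone who leaves early.

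**Protocol 11.3.1** defines the same set with an alternative route in: "or discontinue from study prior to week 28 (visit 16 with a window of -7/+30 days"). Protocol 11.2, which puts the primary analysis at about 122 subjects, says that those who "discontinue from study prior to week 28 (visit 16 with a window of -7/+30 days) will be included in the primary efficacy analysis". **SAP 2.3** repeats this: subjects who "discontinue from study prior to Week 28 (visit 16 with a window of -7/+30 days) will be included in the primary efficacy analysis". The protocol synopsis agrees. SAP 1.2.3, which lists departures from amendment 4, does not mention the mFAS.

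**Who is challenged.** SAP 4.5.1: "all subjects who achieve 300 mg/day AR101 during the up-dosing phase for at least 2 weeks will undergo a post up-dosing DBPCFC". Under protocol 6.1.1.1, subjects who do not tolerate the initial escalation day "will be considered treatment failures and will not initiate home AR101 dosing and should be early terminated from the study".

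**What happens without a challenge.** SAP 2.4 treats subjects who did not reach the dose as non-responders. SAP 5.6.1 does the same for a visit 16 challenge missing for reasons unrelated to COVID-19, and SAP 5.6.2 substitutes the baseline value for the tolerated dose.

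**The concern.** The current texts give two different primary populations. If SAP 3.1 is followed, membership depends on getting through up-dosing to a challenge in the window. That is a post-randomisation outcome, and better tolerance of up-dosing is one of the benefits the protocol hopes dupilumab will bring (sections 1 and 3.2.1). The arms would no longer be compared as randomised. Escalation-day failures and other early leavers would drop out of the denominator, and a benefit that works only by keeping children in up-dosing could not show.

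Other parts of the SAP stop working in that set. The non-responder and baseline-carried-forward rules have almost nobody to act on. The sensitivity analysis restricted to available challenge data nearly repeats the primary analysis. The secondary endpoint of reaching 300 mg/day is met by everyone. SAP 5.6.2 names the FAS for that endpoint, while SAP 10.1 names mFAS and FAS.

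The reason given in the protocol's amendment history for creating the mFAS is "To differentiate the analysis of subjects who up-dosed AR101 per the original protocol plan from those subjects who attended optional visits 15a-f". That purpose does not require removing people who left before those optional visits began.

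**Working it through.** **1. The plan's own figures.** Inputs from protocol 11.2: 104 vs 52 subjects, 65% vs 40%, two-sided Fisher exact test at 5%. Enumerating both binomials gives 81.1% power, which reproduces the stated 80%. For 122 subjects the split is not stated; 2:1 allocation gives about 81:41. Near a 40% placebo rate, the smallest significant result there is 48/81 vs 16/41 = 20.2 points. At 82:40 it is 21.0 points by Fisher and 20.7 by the continuity-corrected formula, against the stated 20.7. Power at 81:41 for 65% vs 40% is 72.2%. These figures belong to the definition that includes discontinuers.

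**2. Assumptions for the comparison.** The documents give no non-completion rate by arm. For placebo plus AR101 I use 20%, from the background statement "Up to 20% of subjects, however, are unable to complete the up-dosing regimen due to side effects". For dupilumab I use 5%, 10% and 20%; these are not in the documents. Non-completers count as failures, and 40% and 65% are the pass rates over all subjects. The pass rate among completers is then

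completer rate = all-subject rate / (1 - non-completion)

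Placebo: 0.40/0.80 = 0.500. Dupilumab: 0.65/0.95 = 0.684; 0.65/0.90 = 0.722; 0.65/0.80 = 0.8125.

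**3. Scenario A: every non-completer leaves the study.** The protocol set keeps all 122. The SAP 3.1 set keeps completers only: 41 x 0.80 = 33 on placebo; 81 x 0.95 = 77, 81 x 0.90 = 73 or 81 x 0.80 = 65 on dupilumab.

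| Non-completion, dupilumab / placebo | Protocol set: difference, power | SAP 3.1 set: n | Difference | Power |
|---|---|---|---|---|
| 5% / 20% | 25.0 points, 72% | 77 + 33 = 110 | 18.4 points | 39% |
| 10% / 20% | 25.0 points, 72% | 73 + 33 = 106 | 22.2 points | 56% |
| 20% / 20% | 25.0 points, 72% | 65 + 33 = 98 | 31.3 points | 87% |

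The smallest significant difference rises from about 20 points at 122 subjects to between 22 and 24 at 98 to 110.

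**4. Scenario B: half of the non-completers leave; the other half stay in the study unchallenged.** Those who stay are outside both versions of the mFAS, so the protocol set shrinks too. Its placebo rate is 0.40/0.90 = 0.444, and its dupilumab rates are 0.65/0.975 = 0.667, 0.65/0.95 = 0.684 and 0.65/0.90 = 0.722. At 79/37, 77/37 and 73/37 (dupilumab/placebo) it shows 22.2, 24.0 and 27.8 points, with power 59%, 66% and 78%. Moving from there to SAP 3.1 changes power by about -20, -10 and +9 points.

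**5. No true difference (40% in both arms over all subjects).**

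| Non-completion, dupilumab / placebo | Completer rates | n | SAP 3.1 set rejects |
|---|---|---|---|
| 5% / 20% | 0.421 vs 0.500 | 77/33 | 9.2% (9.0 points against dupilumab) |
| 20% / 20% | 0.500 vs 0.500 | 65/33 | 3.3% |
| 20% / 5% | 0.500 vs 0.421 | 65/39 | 10.9% (10.7 points in favour of dupilumab) |

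In the first row the protocol set rejects 4.0% under A and 5.7% under B.

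**6. Benefit through tolerability only.** Completers pass at 50% in both arms, and non-completion is 5% vs 20%. Over all subjects: 0.50 x 0.95 - 0.50 x 0.80 = 0.475 - 0.400 = 7.5 points, which the protocol set shows under A. The SAP 3.1 set shows 0.

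**The case against.** The best case for leaving this alone is that it is plainly a slip. SAP 2.3 states the right population, SAP 2.4 and 5.6.1 presuppose it, and the FAS analysis of all randomised subjects is prespecified. I agree that it is probably a slip. But SAP 3.1 is the section that defines the set, and SAP 10.1 refers to the set only by name. The FAS result is supportive, and the gate to the first secondary endpoint (SAP 5.6.3) runs through the primary result. Settling the question after unblinding would be a poor position.

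Three further points stand in part.

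- **The protocol set is itself selective.** Subjects who miss 300 mg/day but stay in the study are outside it, so the fix removes only some of the selection. Scenario B allows for this.
- **Scenario B starts from 81:41, although the documents' 122 already is the protocol set.** Holding that set at 81/41 gives it 63%, 70% and 83% power, against 43%, 58% and 90% under SAP 3.1: changes of about -20, -12 and +6 points. Direction and rough size are unchanged.
- **The rates are at the high end.** In the phase 3 AR101 study cited in protocol 3.2.1, 20.4% discontinued over up-dosing and maintenance together, 12.4% for reasons related to adverse events. With 12.4% on placebo and an assumed 6.2% on dupilumab, all leaving, SAP 3.1 shows 23.6 points with 63% power, and rejects 4.9% when the all-subject rates are equal. The 9.2% and 10.9% need a fourfold imbalance. The 10.9% also needs dupilumab to worsen completion, the opposite of what the protocol expects.

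The per-protocol set adds nothing to the argument: the preliminary list in SAP 10.6 already treats a missing visit 16 challenge as an important deviation.

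**Conclusion.** The concern holds. SAP 3.1 contradicts protocol 11.2, protocol 11.3.1 and SAP 2.3 on who is in the primary analysis, without declaring a change. That conclusion rests on the text alone.

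The size is illustrative, because it depends on assumed non-completion by arm. At 20% on placebo and 5% to 20% on dupilumab, the observed difference moves from 25 points to between 18 and 31, and power from 72% to between 39% and 87%, if all non-completers leave the study. The effect is smaller if only half leave or if the rates are lower. The direction cannot be known in advance. If dupilumab improves completion, the likely cost is lost power and a hidden tolerability benefit; if it worsens completion, the test leans in its favour. This should be corrected before database lock.

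**What to change.** In SAP 3.1, replace the mFAS definition with that of protocol 11.3.1 and SAP 2.3, so that subjects who leave the study before week 28 (visit 16, -7/+30 days) are included. Handle them by the missing-data rules already in SAP 5.6.1 and 5.6.2.

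State that two groups stay outside the mFAS and inside the supportive FAS analysis: subjects still in the study without a challenge in the window, and subjects challenged after it. Adding one group without the other would select on outcome. Report their numbers and reasons by arm, and say that the non-responder statement in SAP 2.4 reaches the first group only in the FAS.

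Name one primary population for the endpoint of reaching 300 mg/day and use it in both SAP 5.6.2 and SAP 10.1. If it is the mFAS, say that subjects still in the study who never reached the dose are not in it.

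The cost is one clause and one population name, plus blinded confirmation of discontinuation status and timing before database lock. No new data and no protocol amendment are needed, and the stated 122 subjects and 20.7 points would then describe the set actually analysed.
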